5.1.5.1. Criteria to Resume Nivolumab Treatment

Please see Table 2 in Section 5.1.5. for guidance on resuming treatment.

Before re-initiating treatment in a participant with a dosing delay lasting > 12 weeks, the Medical Monitor (or designee) must be consulted. Tumor assessments should continue as per protocol even if dosing is delayed. Periodic study visits to assess safety and laboratory studies should also continue every 6 weeks or more frequently if clinically indicated during such dosing delays.

5.1.5.2. Treatment of Nivolumab-related Infusion Reactions

Since nivolumab contains only human immunoglobulin protein sequences, it is unlikely to be immunogenic and induce infusion or hypersensitivity reactions. However, if such a reaction were to occur, it might manifest with fever, chills, rigors, headache, rash, pruritus, arthralgias, hypotension, hypertension, bronchospasm, or other allergic-like reactions. All Grade 3 or 4 infusion reactions should be reported within 24 hours to the study Medical Monitor/designee and reported as an SAE if it meets the criteria. Infusion reactions should be graded according to NCI CTCAE v5.0 guidelines.

Treatment recommendations are provided below and may be modified based on local treatment standards and guidelines, as appropriate:

For Grade 1 symptoms (mild reaction; infusion interruption not indicated; intervention not indicated):

• Remain at bedside and monitor participant until recovery from symptoms. The following prophylactic premedication are recommended for future infusions: diphenhydramine 50 mg (or equivalent) and/or acetaminophen/paracetamol 325 to 1000 mg at least 30 minutes before additional nivolumab administrations.

For Grade 2 symptoms (therapy or infusion interruption indicated but responds promptly to symptomatic treatment [eg, antihistamines, non-steroidal anti-inflammatory drugs, narcotics, IV fluids]; prophylactic medications indicated for ≤ 24 hours):

- Stop the study drug infusion, begin an IV infusion of normal saline, and treat the participant with diphenhydramine 50 mg IV (or equivalent) and/or acetaminophen/paracetamol 325 to 1000 mg; remain at bedside and monitor participant until resolution of symptoms. Corticosteroid and/or bronchodilator therapy may also be administered as appropriate. If the infusion is interrupted, then restart the infusion at 50% of the original infusion rate when symptoms resolve; if no further complications ensue after 30 minutes, the rate may be increased to 100% of the original infusion rate. Monitor participant closely. If symptoms recur, then no further study medication will be administered at that visit.
- For future infusions, the following prophylactic premedication are recommended:
 diphenhydramine 50 mg (or equivalent) and/or acetaminophen/paracetamol 325 to 1000 mg should be administered at least 30 minutes before nivolumab and/or ipilimumab infusions. If necessary, corticosteroids (up to 25 mg of hydrocortisone or equivalent) may be used.

For Grade 3 or 4 symptoms (severe reaction, Grade 3: Prolonged [eg, not rapidly responsive to symptomatic medication and/or brief interruption of infusion]; recurrence of symptoms following initial improvement; hospitalization indicated for clinical sequelae. Grade 4: Life-threatening consequences; urgent intervention indicated):

• Immediately discontinue infusion of study drug. Begin an IV infusion of normal saline and treat the participant as follows: Recommend bronchodilators, epinephrine 0.2 to 1 mg of a 1:1000 solution for subcutaneous administration or 0.1 to 0.25 mg of a 1:10,000 solution injected slowly for IV administration, and/or diphenhydramine 50 mg IV with methylprednisolone 100 mg IV (or equivalent), as needed. Participant should be monitored until the Investigator is comfortable that the symptoms will not recur. Study drug will be permanently discontinued. Investigators should follow their institutional guidelines for the treatment of anaphylaxis. Remain at bedside and monitor participant until recovery of the symptoms.

In case of late-occurring hypersensitivity symptoms (eg, appearance of a localized or generalized pruritus within 1 week after treatment), symptomatic treatment may be given (eg, oral antihistamine or corticosteroids).

5.1.5.3. Nivolumab Treatment Beyond Disease Progression

Reasons for treatment discontinuation are described in Section 4.5. These include discontinuation for progressive disease per RECIST v1.1 and clinical disease progression in the opinion of the Investigator.

However, accumulating evidence indicates a minority of participants treated with immunotherapy may derive clinical benefit despite initial evidence of PD (Spigel-2017).

Participants treated with nivolumab will be permitted to continue nivolumab treatment beyond initial RECIST 1.1 defined PD, assessed by the Investigator up to a maximum of 24 months from date of first dose as long as they meet the following criteria:

VV-RIM-00381493-1.0 Approved - 27 Nov 2024 GMT-5:00

- Investigator-assessed clinical benefit
- Tolerance of study treatment
- Stable performance status

5.1.6. Method of Assigning Subjects

Each subject will be assigned a unique subject identification (ID) number using an Interactive Web Response System. This number will be recorded on the subject's electronic case report form (eCRF) pages and used to identify the subject throughout the study. Once a subject number is assigned, it cannot be reassigned to any other subject.

5.1.7. Blinding and Unblinding Process

This is an open-label study. A BICR will be used for assessment of the primary efficacy endpoint.

5.2. Prior and Concomitant Medications

IMPORTANT: Please refer to Section 5.1.2.1. for required prophylaxis before CMP-001 injection. Prophylaxis administered before and after CMP-001 dosing will be collected in the electronic data capture (EDC) for each visit.

Please refer to Section 4.4. for prohibited treatments.

Concomitant medications will be assessed continually from 30 days before the first dose of study treatment (W1D1) through 100 days after the last dose of study treatment or until an alternative cancer treatment is initiated, whichever occurs first. Treatment medications for AEs related to study treatment that occur more than 100 days after the last dose of study treatment or until an alternative cancer treatment is initiated, whichever occurs first, will be collected. Subjects who discontinue CMP-001 but remain on treatment with nivolumab will continue to have concomitant medications/treatment medications collected according to the Schedule of Assessments (Table 1).

In addition, at each LTSFU contact, an inquiry will be made regarding the start of any new cancer treatments since the date of the last contact. Prior cancer treatments will be documented on a separate eCRF.

5.3. Treatment Compliance

CMP-001 injections must be performed by qualified, trained site personnel. Any deviations in planned dosing, including fully missed study visits, will be documented in the source documents, verified by the Clinical Research Associate (CRA), and recorded as a protocol deviation as appropriate. Nivolumab will be administered by trained site personnel at the clinic site according to the dosing instructions provided in the nivolumab Investigator's Brochure.

6. STUDY TREATMENT MATERIALS AND MANAGEMENT

6.1. Study Treatments

Nivolumab is an FDA approved drug product for the treatment of several types of cancer in multiple regions including the US (Dec-2014), the EU (Jun-2015), and Japan (Jul-2014). The physical characteristics of nivolumab are found in the nivolumab Investigator's Brochure.

CMP-001 is an investigational study drug and will be provided by the Sponsor. CMP-001 is provided as a 5 mg/mL solution in a single-use vial. Each single use vial will contain either 1 mL extractable volume, for a 5 mg dose of CMP-001, or 2 mL extractable volume, for a 10 mg dose of CMP-001. The physical characteristics and other details about the CMP-001 study drug are found in the IB and the Pharmacy Manual.

At the end of the treatment period, study treatment will no longer be provided to subjects/investigators unless the Sponsor chooses to extend the study. The Investigator should ensure that the subject receives appropriate standard of care to treat the condition under study.

6.2. Study Drug Labeling and Packaging

Details of the study drug labeling and packaging are provided in the Pharmacy Manual. The study drug vials will be labeled with the following information:

- The protocol number
- The kit number
- Number of vials per kit (carton only)
- The batch number of the drug
- The drug name, concentration, and nominal volume per vial
- The recommended storage conditions of the drug
- Cautionary statement to keep away from children
- Cautionary statement indicating that the drug is for investigational use only
- The name and address of the Sponsor

6.3. Study Drug Handling, Storage, Accountability

All study drug vials will be transported, received, stored, and handled in accordance with the carton and vial labels and instructions provided to the site and relevant personnel. The site's SOPs, and applicable regulations will be followed.

Appropriate storage and transportation conditions will be maintained for the study drug vials from the point of manufacture up to delivery. All shipments of study drug vials will include a temperature-monitoring device that records required storage conditions for the vials at regular intervals for the entire time the shipment is in transit.

Upon receipt by the site, the designated site personnel will examine the shipment and temperature-monitoring devices to verify the study drug vials were received in acceptable condition. Vials received in acceptable condition should be stored at the specified temperature (2°C to 8°C) in a locked area accessible only to designated site personnel until dispensed. Dispensed study drug vials will be stored in a limited access area under

appropriate environmental conditions as defined in the Pharmacy Manual. Vials not received in acceptable condition should be immediately quarantined at the appropriate temperature (2°C to 8°C), and the site personnel must immediately notify the IQVIA CRA. Such study drug vials may not be used until IQVIA representatives (eg, IQVIA CRA) has conveyed a determination about these specific study drug vials.

The designated site personnel will be responsible for maintaining accurate records of the quantity and dates of all study drug supplies received, dispensed, and returned, in accordance with applicable regulations and the site's SOPs. The quantity of study drug lost, destroyed, or otherwise unaccounted for must also be accounted for and documented.

All original study drug product, whether empty or containing study drug, will be kept at the site. Study drug vials are single-use only; therefore, contents of partially used study drug vials may not be dispensed again, even to the same subject, nor relabeled or reassigned for use by other subjects. Unused study drug vials will be available for verification by the study monitor. Once dispensed, used study drug vials will be stored in a limited access area under appropriate environmental conditions.

At each investigational site closeout visit and end of clinical trial, a final study drug vial accountability review and reconciliation must be completed by the Sponsor or its representatives and any discrepancies must be investigated and their resolution documented. All study drug product vials will be destroyed at the investigational site as per institutional SOPs, after site closeout has been completed or if approved by the Sponsor or its representative as required by the site (ie, space limitations, policy) once drug accountability is conducted by the IQVIA Biotech CRA. A copy of the site destruction SOP must be maintained on file and available for the IQVIA Biotech CRA. If unable to destroy on site, please inform the IQVIA Biotech CRA.

Details of the study drug storage and handling are provided in the Pharmacy Manual.

6.4. Study Drug Dispensing

CMP-001 will be dispensed, prepared, and administered according to the Pharmacy Manual and site SOPs. Details regarding the preparation, dilution, and administration of the CMP-001 is outlined in the Pharmacy Manual. Only eligible subjects participating in the study may receive CMP-001. CMP-001 study drug is dedicated to each study and is labeled specifically for each CMP-001 study. Only authorized and qualified site staff may dispense, prepare, or administer CMP-001.

Nivolumab will be dispensed, prepared, and administered according to the Pharmacy Manual and site SOPs.

7. STUDY ASSESSMENTS AND PROCEDURES

7.1. **Procedures and Assessments**

Assessments to be performed at Screening and throughout the study are specified in the Schedule of Assessments Table 1.

7.1.1. Informed Consent

Subjects must sign a written informed consent form(s) (ICF) before the initiation of any study procedures and thereafter if there are any ICF changes. Subjects will be given a signed copy of the ICF to take home. Subjects unable to provide written informed consent on their own behalf will not be eligible for the study.

7.1.2. Eligibility Criteria

Subjects must meet all inclusion and exclusion criteria to be eligible for the study. Refer to Section 4.

7.1.3. Demographics

Demographic data will be collected during Screening. Demographic data will include date of birth, sex, ethnicity, and race (ie, white, black or African American, Asian, American Indian/Alaskan Native, Native Hawaiian/other Pacific Islander, or other).

7.1.4. Melanoma History

Eligible subjects must have been diagnosed with a histopathologically-confirmed diagnosis of metastatic malignant or unresectable melanoma. Subjects with uveal, acral, or mucosal melanoma are not eligible.

Documentation, including radiographic and/or photographic images at baseline or at the time of response and from 2 consecutive scans separated by at least 4 weeks that demonstrate confirmed disease progression during or within 12 weeks of prior treatment that included PD-1 blockade with an FDA-approved PD-1 blocking antibody, must be reviewed by the investigator at Screening to meet eligibility (see Section 7.2.). These images should be sent/uploaded for central review for post-enrollment verification and endpoint assessment. If necessary, additional prior images may be requested for central review.

For subjects with relapse/recurrence on or after adjuvant PD-1 blocking antibody, a histological confirmation of recurrence is required. In such cases required images include imaging at initiation of adjuvant therapy demonstrating no evidence of disease and images demonstrating relapse/recurrence; images are not required for confirmation of progression. These images should be sent/uploaded for central review.

At Screening, a detailed melanoma history will be obtained, including date of initial diagnosis, American Joint Committee on Cancer (AJCC) melanoma cancer staging at diagnosis, and BRAF mutation status including treatment with a kinase inhibitor targeted for BRAF mutation (with or without a MEK inhibitor). BRAF mutation status must be assessed with an FDA-approved test. Sites should refer to the Eighth Edition AJCC Cancer Staging Manual (Amin-2017) for cancer staging.

Programmed death-ligand 1 expression status from prior biopsies, if available, will be recorded in the EDC.

Amendment 2 (Version 3.0) 26 August 2021 61

Confidential

VV-RIM-00381493-1.0 Approved - 27 Nov 2024 GMT-5:00

7.1.5. **Prior Cancer Treatments**

Details regarding all prior cancer treatments, including drug generic name, dose (if available), route of administration, start date, end date, best response, and last response to prior therapy, will be documented on a separate page in the EDC. Data on prior surgical procedures related to melanoma will also be captured in the EDC.

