4.1. Inclusion Criteria

Subjects enrolled in the study must meet all of the following inclusion criteria to be eligible.

- 1. Histopathologically-confirmed diagnosis of malignant melanoma that is metastatic or unresectable at Screening.
- Known BRAF mutation status; if BRAF V600 mutation positive, must have had prior treatment with a local Health Authority approved BRAF inhibitor, with or without MEK inhibitor. Patients with BRAF V600 mutations who refuse a BRAF inhibitor will not be eligible.
- 3. Refractory to PD-1 blockade either as monotherapy or in combination with other therapies, as defined by the following criteria:
 - a. Received treatment with a Food and Drug Administration approved PD-1 blocking antibody for 12 weeks or longer.
 - b. Have PD (according to RECIST v1.1) within 12 weeks of the last dose of a PD-1 blocking antibody, either as monotherapy or in combination with other agents.
 - Evidence of confirmed PD must be established by Investigator assessment at least 4 weeks after the initial date of PD. The confirmatory assessment may serve as the Baseline for this study if completed within 30 days before the start of study treatment.
 NOTE: in subjects with histologically confirmed recurrence on or after adjuvant PD-1 blocking antibody, confirmatory imaging is not required.
- 4. Measurable disease, as defined by RECIST v1.1 and all of the following:
 - a. At least 1 accessible lesion amenable to repeated IT injection.
 - b. One or more measurable lesions at least 1 cm in diameter that are not intended for CMP-001 injection and can be followed as target lesions per RECIST v1.1.
 - c. Documented disease progression in any lesion that was previously radiated in order to serve as a target lesion.
- 5. Able to provide tissue from a core or excisional/incisional biopsy (fine needle aspirate is not sufficient). A fresh tissue biopsy (within 90 days before the start of study treatment) is preferred but an archival sample is acceptable (as a substitute) if no intervening therapy was received. If the Investigator believes it is unsafe to perform a biopsy, the subject may be considered eligible after discussion with the Medical Monitor if tissue and/or prior assessments are available to determine programmed death-ligand 1 expression.
 - 6. NOTE: for tissue sampling details, please refer to the laboratory manual.

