9.3.4. Melanoma History

Melanoma history (time since initial diagnosis, tumor stage, nodal status, and metastatic disease status at time of initial diagnosis) will be summarized using descriptive statistics for the ITT Analysis Set and listed by subject. Melanoma history will be captured on a separate eCRF in the EDC system.

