### Statistical Analysis Plan

Regeneron Pharmaceuticals Inc. / Protocol: CMP-001-010 IQVIA Biotech (Confidential) Project # RZA44091

- Clinical staging
  - Clinical staging at diagnosis
  - Tumor status
  - Nodal status
  - Metastatic disease status
- Pathologic staging
  - Pathologic staging at diagnosis
  - Tumor status
  - Nodal status
  - Metastatic disease status

Prior Primary Cancer Treatments. Listings of key data related to prior melanoma treatments will be provided for ITT Analysis Set, and include the following information:

- Number of Lines of Prior Systemic Therapies: summarized categorically  $(1, 2, \ge 3)$
- Any Prior Therapy
  - o Prior Systemic Therapy
  - o Prior Radiotherapy
  - o Prior Cancer-related Surgery
- Reason for Discontinuation from Any Prior Systemic Therapy
- Regimen Best Response on Any Prior Systemic Therapy
- Duration of Exposure to Any Prior Systemic Therapy (months), summarized continuously
- Administrative Setting of Prior Systemic Therapy
- Time since Completion of Prior Adjuvant Systemic Therapy to First Dose Date (< 6 months; ≥ 6 months)

All prior melanoma treatments will be captured in the EDC separately from other prior medications. Combination treatments should be considered as a single regimen and recorded as such in the EDC. Details regarding all prior melanoma treatments, including drug generic name, start date, end date, regimen best response to prior therapy, and administrative setting, as well as key data related to prior melanoma treatments, will be listed by subject for ITT Analysis Set.

Data on Prior Cancer Radiation and Prior Cancer Surgery will be captured on different pages of eCRF and presented in separate by-subject data listings.

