### D. Efficacy Analysis on Subgroups of Subjects

The below subgroup analysis (not limited to) for efficacy will be explored using forest plots of the calculated ORRs with their 95% CIs.

- Serum LDH at diagnosis (Elevated, Normal)
- BRAF mutation (Yes, No)
- Number of Lines of Prior Therapies  $(1, 2, \ge 3)$ . Note the categories can be modified based on the data).
- Best Response to Prior Anti-PD-L1 (CR, PR, SD, PD, NE, NA, Unknown)
- Clinical Disease Stage at diagnosis (M0/M1a/M1b, M1c/M1d)

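### SAP VIII.D splits ORR by M category at initial diagnosis, so the exploratory stage subgroup can misplace subjects whose disease at study entry counts as M1c/M1d

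*Protocol*

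**What the plan says.** Protocol 7.1.4 lists, among the items of melanoma history taken at Screening, "including date of initial diagnosis, American Joint Committee on Cancer (AJCC) melanoma cancer staging at diagnosis, and BRAF mutation status", and refers sites to the AJCC 8th edition. Protocol 9.3.4 settles which diagnosis is meant: it summarises "tumor stage, nodal status, and metastatic disease status at time of initial diagnosis". SAP VII.A carries this forward, with "Clinical staging at diagnosis" and a matching pathologic item.

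SAP VIII.D uses the same time point to group ORR: "Clinical Disease Stage at diagnosis (M0/M1a/M1b, M1c/M1d". It describes the exercise in these terms: "The below subgroup analysis (not limited to) for efficacy will be explored using forest plots of the calculated ORRs with their 95% CIs". The serum LDH subgroup in the same list is also defined at diagnosis.

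Eligibility is set at a different time. Protocol 4.1 requires "Histopathologically-confirmed diagnosis of malignant melanoma that is metastatic or unresectable at Screening", with progression after at least 12 weeks of PD-1 therapy. For subjects who relapse on or after adjuvant PD-1 therapy, Protocol 7.1.4 asks for "imaging at initiation of adjuvant therapy demonstrating no evidence of disease and images demonstrating relapse/recurrence". No section of either document plans an M category at study entry.

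**The concern.** A stage subgroup in a single-arm trial is read as a statement about the disease that was treated. Here the grouping variable describes an earlier state. Between first diagnosis and entry every subject has progressed or recurred, and the protocol allows for advanced disease at entry. Protocol 5.1.2.3.1 foresees visceral tumors. Protocol 4.2 excludes CNS metastases only if they are untreated, symptomatic or enlarging. Protocol 7.2.3.2 provides for subjects with current or prior brain metastases.

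At stake is whether the forest plot can help a reader judge if responses come mainly from subjects with limited disease. That matters because Protocol 9.5.1 sets the ORR against an outside benchmark of 7%, and this is the only listed ORR subgroup based on extent of disease.

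**Working it through.** **Reading the rule through.** The plan gives no stage distribution and no expected ORR by stage, so there is no figure of its own to reproduce on this point. The misplacement follows from the text:

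1. Stage is fixed at initial diagnosis (Protocol 7.1.4 and 9.3.4; SAP VII.A).
2. The ORR split uses that stage (SAP VIII.D).
3. Entry requires later metastatic or unresectable disease, and neither visceral metastases nor treated, stable CNS metastases are excluded (Protocol 4.1, 4.2, 5.1.2.3.1).
4. So a subject who was M0 at diagnosis and whose disease counts as M1c or M1d at entry is plotted as M0/M1a/M1b.

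**Illustrating the size.** The only document figure used is N = 44 (SAP II.C). The rest is assumed: a true ORR of 30% for M0/M1a/M1b at entry and 10% for M1c/M1d at entry, with ORR depending only on entry stage, and subjects who were M1c/M1d at diagnosis still being so at entry.

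Let s be the share of the recorded M0/M1a/M1b group that is M1c/M1d at entry. Then:

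- recorded lower-stage ORR = 30% − 20 points × s
- apparent difference = 20 points × (1 − s)

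*Set A.* Let e be the M1c/M1d share at entry (40% to 60%) and d the share at diagnosis (5% to 20%). Then s = (e − d)/(1 − d).

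*Set B.* Let e be 40% to 60%, and let m be the proportion of those subjects staged lower at diagnosis (25% to 75%). Then s = e·m/[(1 − e) + e·m].

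| Case | Recorded M0/M1a/M1b (n) | Of these, M1c/M1d at entry (n) | s | Recorded ORR | Apparent difference | Recorded M1c/M1d (n) |
|---|---|---|---|---|---|---|
| A: e 40%, d 20% | 35.2 | 8.8 | 25% | 25.0% | 15.0 points | 8.8 |
| A: e 60%, d 5% | 41.8 | 24.2 | 58% | 18.4% | 8.4 points | 2.2 |
| B: e 40%, m 25% | 30.8 | 4.4 | 14% | 27.1% | 17.1 points | 13.2 |
| B: e 60%, m 75% | 37.4 | 19.8 | 53% | 19.4% | 9.4 points | 6.6 |

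These rows give the smallest and largest dilution in each set. Across both sets, a true 20-point difference shows as 8.4 to 17.1 points. The recorded M1c/M1d group runs from 2.2 (set A, d = 5%) to 19.8 subjects (set B, e = 60% and m = 25%).

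**Precision under either definition.** With 22 subjects in each entry-stage group, 30% and 10% correspond to about 7 and 2 responders. The 95% Clopper-Pearson intervals are 13.9% to 54.9% for 7/22 and 1.1% to 29.2% for 2/22, which overlap. Small diagnosis-stage groups do no better: 0/4 gives 0% to 60.2% and 1/9 gives 0.3% to 48.2%.

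**The case against.** The strongest reply is that little hangs on this. Enrolment stopped early, SAP II.C and IV make all analyses exploratory, SAP VI.H sets no test size, and the subgroup list is open-ended. The primary ORR and its interval (SAP VIII.B) do not use stage. At N = 44 even a correctly timed subgroup would separate the groups poorly. All of this stands and limits the importance of the point. It does not make the grouping right: a wide interval is imprecise about the intended question, whereas staging at the wrong time answers another one.

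A second reply is that entry extent is not ignored. SAP VII.A plans disease type at enrollment, tumor burden, measurable disease, ECOG, other key baseline information and a summary of CNS screening, and SAP VIII.C lists all lesion assessments. That also stands. What is missing is an entry M category and its use in the ORR split.

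Several stronger readings are tempting but not supported:

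- *Stage at entry is never recorded.* The list in Protocol 7.1.4 is open-ended, and the case report form is not among the documents.
- *The M1c/M1d group will be nearly empty.* This depends on an assumed share at diagnosis. The two sets above span about 2 to 20 subjects.
- *Most adjuvant-route subjects fall in the lower group.* Protocol 7.1.4 requires no evidence of disease when adjuvant therapy began. It gives neither their M category at diagnosis nor their number.
- *Any visceral metastasis at entry is misplaced.* Neither document reproduces the AJCC M definitions, so the point covers only disease that would count as M1c or M1d.

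**Conclusion.** The point holds for one exploratory subgroup. Followed as written, SAP VIII.D can put subjects with M1c/M1d disease at entry in the M0/M1a/M1b group, which would dilute an ORR difference by extent of disease. The dilution to roughly 8 to 17 of 20 points is an illustration. It rests on assumed stage shares and response rates, and on no movement to a lower category between diagnosis and entry. It also makes no allowance for the entry limits on LDH, CNS disease and rapid progression in Protocol 4.1 and 4.2. The actual size cannot be known from the documents.

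A reader might infer that the primary ORR is biased or that the protocol's data collection must be amended. Neither follows. The primary result does not depend on stage, and the last subject enrolled on 30 June 2022 (SAP II.C), so changing the Screening history now would collect nothing prospectively. The correction is worth making because it is cheap and makes the subgroup describe the disease treated.

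**What to change.** Change the SAP only.

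1. In VIII.D, replace clinical stage at diagnosis with AJCC 8th edition M category at study entry, keeping the M0/M1a/M1b versus M1c/M1d split. Derive it from the sites of baseline target and non-target lesions, the required baseline CNS imaging and, so far as the staging manual uses it, the last pre-dose LDH. State the derivation rule in the SAP.
2. Add this variable to the Baseline Disease Characteristics summary in VII.A, and keep stage at diagnosis in the melanoma history as history only.
3. Make the same timing change to the adjacent serum LDH subgroup. Use the pre-dose value under the baseline definition in SAP VI.B; Protocol 4.1 already requires LDH within 3 weeks before the first dose.

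The cost is revised wording and one derived variable, with no new assessment. The downside is that some subjects may be unclassifiable if lesion-site data are incomplete; show them as a separate category. The change will not narrow the intervals.
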